A priori power analysis was conducted using G*Power 3.1.9 to determine the minimum sample size required to find statistical significance using a 3 (group) x 4 (time) repeated measures analysis of variance (i.e., a mixed-model ANOVA). With a desired level of power set at .80, an alpha (α) level at .05, and a moderate effect size of .25 (f), it was determined that a minimum of 30 total participants would be required to ensure adequate power (Cohen, 1988).

Mean heart rate, mean blood pressure, mean scores on STAI, and academic performance score (Pass/Fail) will be calculated for all groups. Demographic data will be analyzed in terms of frequencies and comparisons between groups. For RQ1: Pearson's correlation will examine the relationship between the music intervention on stress, anxiety, and academic performance. For RQ2: To measure anxiety, STAI mean scores will be analyzed. For RQ3: To measure stress levels, the mean heart rate and mean blood pressure will be analyzed. For RQ4: To assess academic performance, Pass/fail scores will be looked at. MANOVA will be considered for data analysis since there is one independent variable (music intervention) and multiple dependent variables. If any variables are not correlated, running a repeated-measures ANOVA to detect any overall differences between any related means would be considered. A paired samples t-tests could also be used for pre-and post-comparisons of vital signs. Using a Chi-Square test can also be beneficial in determining any differences in demographics and anxiety and/or stress. Alpha will be set at 0.05 for the study.

Item 7 Risks Section:

Complete the following table to describe the risks of all **research procedures** listed in Step 2, Institutional Form (items 28-34). *Do not list risks of Routine care procedures here.*

N/A, Risks are described in the informed consent document – do not complete this table.

Research procedures	Risks

example:
 
 • History and physical • Questionnaire • Laboratory tests 	
List the reasonably expected risks under the following categories as appropriate:

Add or delete rows as needed	
Vitals Signs obtained via SmartWatch	
Serious and likely;
 
 ○ None 
Serious and less likely;
 
 ○ None
Heart Rate Blood Pressure	
Demographic data form, paper and pencil	
Serious and likely;
 
 ○ None

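### The plan makes repeated-measures ANOVA depend on outcomes being uncorrelated, which is the wrong trigger, and the sentence names no arm-by-time test of music

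*Combined protocol and SAP*

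**What the plan says.** The Data Analysis Plan in Item 6 does two things that bear on this point.

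- **Sample size.** It powers the study on a "3 (group) x 4 (time) repeated measures analysis of variance", which it glosses as a mixed model, with power .80, alpha .05 and f = .25. It concludes that "a minimum of 30 total participants would be required to ensure adequate power".
- **Analysis.** It first says that "MANOVA will be considered for data analysis since there is one independent variable (music intervention) and multiple dependent variables". It then adds: "If any variables are not correlated, running a repeated-measures ANOVA to detect any overall differences between any related means would be considered". The next sentence offers paired t-tests for vital signs before and after, without mentioning a comparison between arms.

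The Step-by-Step Methods in Item 6 give the measurement schedule. STAI Y-1, heart rate and blood pressure are taken before the 15-minute period, after it, and again after the skills assessment. Pass/fail is recorded once, at the end. Control students sit quietly for the same 15 minutes and then take the same assessment. Phase 1 has up to 10 students per arm (20 in all). Phase 2 takes the Summer 2022 cohort of about 108.

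**The concern.** Three things are wrong with the fallback sentence.

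1. **The trigger.** Repeated-measures ANOVA is needed when the same variable is read more than once in the same student. That is true here of STAI Y-1, heart rate and blood pressure by design. Whether STAI correlates with heart rate has no bearing on it. Uncorrelated outcomes would argue for analysing each outcome separately, which is a different matter from adding a time factor.
2. **The target.** The sentence looks for differences among related means and names neither group nor group-by-time. Both arms wait and both are then tested, so both may change over time for reasons unrelated to music. A test of change over time alone cannot separate music from waiting.
3. **The criterion.** The plan does not say which variables, at which time, by what test or at what cut-off the lack of correlation is judged.

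At stake is whether a change common to both arms could be reported as an answer to RQ2 or RQ3, which ask whether music lowers anxiety and stress before the assessment.

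**Working it through.** **Step 1. Reproduce the stated N.** From the plan: k = 3 groups, m = 4 times, f = .25, alpha = .05, power = .80. Assumed, because the plan does not give it: correlation among repeated measures rho = .5, with sphericity.

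For the group-by-time interaction, λ = f²·N·m/(1 − rho), df1 = (k − 1)(m − 1), df2 = (N − k)(m − 1).

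At N = 30: λ = .0625 × 30 × 4 / .5 = 15, df1 = 2 × 3 = 6, df2 = 27 × 3 = 81. Power = .809, and 30 is the smallest equal-group N that reaches .80. The stated figure is reproduced.

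Other tests in the same 3 × 4 layout give other sample sizes:

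| Test | N at rho = .5 | N at rho = 0 |
|---|---|---|
| Group-by-time | 30 | 57 |
| Time main effect | 24 | 45 |
| Group main effect | 102 | 42 |

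So, in the plan's own layout, the test that gives 30 is group-by-time. (The methods describe two arms and three measurement times rather than 3 × 4. That is a separate point.)

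**Step 2. The literal fallback when music does nothing.** Two arms, three times, rho = .5. Assume both arms shift by d SD after the wait and stay there: means 0, −d, −d. The squared deviations from their mean sum to (2/3)d². For the time test, λ = N·(2/3)d²/(1 − rho), with df 2 and 2(N − 2). For example, N = 30 and d = .5 give λ = 30 × .1667/.5 = 10.

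| N | d | λ | Time test significant | Group-by-time (simulated) |
|---|---|---|---|---|
| 20 | 0.3 | 2.4 | 25% | 5% |
| 20 | 0.5 | 6.67 | 59% | 5% |
| 30 | 0.3 | 3.6 | 36% | 5% |
| 30 | 0.5 | 10 | 79% | 5% |
| 108 | 0.3 | 12.96 | 90% | 4% |
| 108 | 0.5 | 36 | about 100% | 5% |

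A shift at the second assessment only (0, −d, 0) has the same sum of squares, hence the same time-test results. With no shift at all, every test rejects at about 5%.

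A paired t-test within the music arm (N/2 students) has the same weakness. Simulated on the same data, for d = 0.3 and 0.5, it is significant in 13% and 29% of trials at N = 20, 19% and 44% at N = 30, and 58% and 95% at N = 108.

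**Step 3. How often the trigger would fire.** Assume three outcomes (STAI, heart rate, one blood pressure value) with a common true correlation r, and take 'uncorrelated' to mean p > .05 for at least one of the three pairs. Simulation gives:

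| N | r = .3 | r = .5 |
|---|---|---|
| 20 | 95% | 62% |
| 30 | 89% | 36% |
| 108 | 26% | about 0% |

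At pilot size, then, outcomes that truly are correlated would often be judged not to be. At the Phase 2 size this is much rarer.

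**The case against.** The strongest reply is that the same section describes the repeated-measures ANOVA as a group-by-time mixed model when it sets the sample size. Read with that, the fallback has a group factor, and its interaction holds its error at about 5% under a shared change. The rates in Step 2 then do not apply. This stands as far as intent goes: a reader might infer that the fallback is definitely aimed at the shared time change, and the documents do not establish that. It does not rescue the sentence, which names no such term and puts its target in words that fit a time test.

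A second reply is that the sentence follows directly on MANOVA and may only mean that, if outcomes are unrelated, each should be analysed alone, which for repeated readings is a repeated-measures ANOVA. That is a sensible thought, but it would not justify withholding the repeated-measures analysis when outcomes are correlated.

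Third, nothing is binding: the plan puts MANOVA, repeated-measures ANOVA and t-tests forward only as possibilities and gives no cut-off for correlation. A reader might conclude that chance picks the analysis. That goes too far. Analyst judgement enters as well, the p > .05 rule is an assumption of this review, and at N = 108 with r = .5 the trigger almost never fires.

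Finally, a reader might conclude that MANOVA must be removed as a weak test. The documents do not support that either. They do not say which readings would enter it, and a between-arm MANOVA on post-wait values would be a legitimate test of music.

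**Conclusion.** The point holds in limited form. The correlation condition is the wrong reason to use or not use repeated-measures ANOVA; this follows from the measurement schedule and needs no assumption. It is equally plain from the text that the sentence names no group or group-by-time term, so that it does not match the test that reproduces N = 30 (with rho = .5 assumed).

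The size of the consequence is conditional. If the sentence is applied literally, a shared change of 0.3 to 0.5 SD makes the test significant without any music effect in about a quarter to three fifths of trials at the pilot maximum, and in 90% or more at the Phase 2 size. The shared change, rho = .5, the between-outcome correlations, the p > .05 cut-off, normal outcomes and no clustering by sign-up group are all assumptions not found in the documents. The plan should be changed, but what is shown is an ambiguity that permits a misleading test, not a commitment to one.

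**What to change.** - Delete the correlation condition.
- For STAI Y-1, heart rate and blood pressure, fit one arm-by-time model per outcome, whatever the correlation between outcomes.
- Name the between-arm contrast in change from baseline to post-wait as the test of music for RQ2 and RQ3.
- State that the overall time effect and any within-arm paired t-tests are descriptive.
- Compare pass/fail, which is measured once, between arms in a separate analysis for RQ4.
- Keep MANOVA, if wanted, as a secondary analysis, and say which readings enter it.

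The cost is a few sentences of analysis-plan wording. No extra data, visits or students are needed.
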